10.7 ELECTROCARDIOGRAM EVALUATIONS

Descriptive statistics for ECG findings (sinus rhythm [present/absent], heart rate, PR interval, QRS duration, QT interval, interpretation [normal/abnormal]) will be presented by treatment group. Continuous variables will also be presented as the raw values and change from the respective baseline will be presented for each post-baseline assessment by treatment received at the time of the visit. Additionally, summary statistics for continuous variables will be presented for the change in each parameter from the Baseline Visit for Treatment Period 1 to the Baseline Visit for Treatment Period 2. Whenever more than 1 ECG evaluations are recorded on the same day, the data summaries will use the average of these readings.

In addition, a summary of subjects with treatment-emergent abnormal values will be presented by treatment received at the time of the evaluation. Presentation will be made in order of decreasing incidence by type of abnormality with the number and percentage of subjects who experienced the type of abnormality.

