# 3.3.2.4 12-Lead Electrocardiogram

A 12-lead ECG will be recorded (following at least 5 minutes of rest) during Screening Visit 1 and at study visits at Study Weeks 1, 6, 12, 14, 19, & 25 or ET in the **Original Crossover Design**, or if applicable, Screening Visit 1 and at study visits at Study Weeks 1, 6, & 12 or ET in the **Contingent Parallel Design**. No other measurements or procedures should be performed during the rest period. The ECG assessment must be performed prior to dosing during Screening Visit 1 and at Study Weeks 1 & 14 in the **Original Crossover Design** or during Screening Visit 1 and at Study Week 1 in the **Contingent Parallel Design**. Recordings should include lead II as a rhythm strip and contain at least 5 electrocardiographic wave (QRS) complexes.

Parameters to be collected include rhythm, HR, PR interval, QT interval, QRS duration, and any clinically significant abnormalities. Any clinically significant changes from Screening Visit 1 should be reported as AEs.

In the event of Sponsor-approved telemedicine visits, the 12-lead ECG assessment will not be performed.

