# 10.3.4 Safety Analyses

The safety of inhaled treprostinil compared to placebo will be evaluated on the following parameters: AEs, clinical laboratory assessments, ECGs, PE findings, oxygenation, PFTs, vital sign measurements, and at-home spirometry.

All AEs as recorded by the Investigators will be assigned a Medical Dictionary for Regulatory Activities (MedDRA) Preferred Term and System Organ Class by the Sponsor for reporting purposes. The summary of AEs will include the number and percentage of subjects, as well as the number of events reported for each Preferred Term. No inferential analyses are planned for the AEs.

Data collected prior to dosing will serve as baseline values for the evaluation of data collected during the Treatment Period. Summary statistics will be calculated for measured values and changes from baseline values. Treatment-emergent changes in clinical laboratory evaluations, ECGs, oxygenation, PFTs, at-home spirometry, and vital sign measurements will be summarized by treatment group. No inferential analyses are planned on these safety endpoints.

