MAR	Missing at random
MET	Metabolic equivalent task
MedDRA	Medical Dictionary for Regulatory Activities
MMRM	Mixed-effect model for repeated measures
mPAP	Mean pulmonary artery pressure
MVPA	Moderate to vigorous physical activity
NT-proBNP	N-terminal pro-brain natriuretic peptide
PEF	Peak expiratory flow
PFT	Pulmonary function test
PGA	Patient global assessment
PH	Pulmonary hypertension
PH-COPD	Pulmonary hypertension due to chronic obstructive pulmonary disease
PR	Electrocardiographic wave of P-R interval
PT	Preferred Term
PVR	Pulmonary vascular resistance
QID	4 times daily
QOL	Quality of life
QRS	Electrocardiographic wave of QRS interval
QT	Electrocardiographic wave of QT interval
RHC	Right heart catheterization
RVSP	Right ventricular systolic pressure

SAE	Serious adverse event
SAP	Statistical Analysis Plan
SGRQ	St. George's Respiratory Questionnaire
SOC	System Organ Class
SpO ₂	Saturation peripheral capillary oxygenation
TLC	Total lung capacity
UCSD SOBQ	University of California San Diego Shortness of Breath Questionnaire
WHO	World Health Organization

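### The ECG safety tables summarise only uncorrected QT, although the heart rate needed to correct it is recorded on the same ECG; adding QTcF is a cheap improvement

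*SAP*

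**What the plan says.** Protocol 3.3.2.4 fixes what is recorded on each 12-lead ECG: "Parameters to be collected include rhythm, HR, PR interval, QT interval, QRS duration, and any clinically significant abnormalities".

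SAP 10.7 then tabulates sinus rhythm and "heart rate, PR interval, QRS duration, QT interval, interpretation [normal/abnormal]) will be presented by treatment group". It adds: "Continuous variables will also be presented as the raw values and change from the respective baseline". It also promises "a summary of subjects with treatment-emergent abnormal values will be presented by treatment received at the time of the evaluation", ordered by type and incidence, with no QT criterion given. Several ECGs on one day are averaged. The replacement text for the Contingent Parallel Design in SAP 12.4.7 repeats the same variable list.

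The SAP abbreviation list has an entry for QT, "Electrocardiographic wave of QT interval", and none for a corrected QT. SAP 10.7 shows no redaction in the public copy, so the gap is not a matter of hidden text in that section. Protocol 10.3.4 sets the status of these tables: "No inferential analyses are planned on these safety endpoints".

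**The concern.** The QT interval shortens as heart rate rises, whether or not repolarisation has changed. A change in uncorrected QT therefore mixes two things: any repolarisation effect, and any difference in heart rate between the two ECGs. The plan records both quantities on the same tracing but tabulates them as separate variables and never combines them.

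Two cases need to be kept apart.

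- **Rate variation common to both arms.** Differences in rest, concurrent bronchodilator use or illness move QT from visit to visit. With randomisation, and with each subject receiving both treatments under the crossover, this widens the spread of QT changes but does not shift the treatment comparison.
- **A treatment-related rate change.** If active drug changes heart rate relative to placebo, the QT comparison shifts with it. A rate rise hides prolongation and a rate fall imitates it.

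ECGs are a named safety objective, so the QT rows are likely to be read as evidence on repolarisation. At stake is whether those rows can bear that reading without further work.

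**Working it through.** The plan states no QT figure, threshold or precision target, so there is nothing of its own to reproduce. The check compares the sections and then sizes the effect.

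**Sections.** Heart rate and QT are both collected (Protocol 3.3.2.4) and both summarised (SAP 10.7 and its 12.4.7 replacement). No correction formula, joint analysis of QT and heart rate, or QT category appears in either version. The inputs to a correction exist; only the derivation is missing.

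**Assumptions (not in the documents).** True corrected QT 400 ms; starting heart rate 70 bpm; rises of 5 and 10 bpm and a fall of 10 bpm.

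**Formulas.** Fridericia: QT = QTcF × (60/HR)^(1/3). Bazett: QT = QTcB × (60/HR)^(1/2).

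**Corrected QT held constant (Fridericia):**

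- 70 bpm: 400 × (60/70)^(1/3) = 400 × 0.9499 = 380.0 ms
- 75 bpm: 400 × (60/75)^(1/3) = 400 × 0.9283 = 371.3 ms, a fall of 8.6 ms before rounding
- 80 bpm: 400 × (60/80)^(1/3) = 400 × 0.9086 = 363.4 ms, a fall of 16.5 ms
- 60 bpm: 400 × 1 = 400.0 ms, a rise of 20.0 ms

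Under Bazett, 70 to 80 bpm gives 370.3 to 346.4 ms, a fall of 23.9 ms.

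**Corrected QT rise hidden by an unchanged QT.** This is a different quantity from the fall above. If QT is still 380.0 ms at 80 bpm, then QTcF = 380.0/0.9086 = 418.2 ms. The hidden increase is 418.2 − 400 = 18.2 ms, about 18 ms.

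**Range under other assumptions (corrected QT 420 ms, starting rate 70 or 80 bpm):**

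| Rate change | Change in QT, corrected QT constant: Fridericia | Same: Bazett | Corrected QT rise hidden if QT unchanged: Fridericia | Same: Bazett |
|---|---|---|---|---|
| +5 bpm | −7.6 to −9.1 ms | −10.9 to −13.2 ms | 8.6 to 9.8 ms | 12.9 to 14.7 ms |
| +10 bpm | −14.7 to −17.4 ms | −20.8 to −25.1 ms | 16.8 to 19.1 ms | 25.5 to 29.0 ms |
| −10 bpm | +17.4 to +21.0 ms | +25.1 to +31.2 ms | not applicable | not applicable |

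Near 70 bpm the Fridericia result is roughly 1.7 ms of QT per bpm (16.5/10 = 1.65; 8.6/5 = 1.72), so even modest rate differences move QT by several milliseconds.

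**The case against.** The strongest reply is that nothing in the documents points to a heart-rate effect. Protocol 1.2.1 and 1.4 describe prostacyclin as raising cardiac output while leaving heart rate unchanged. Protocol 1.2.3 reports no remarkable treatment-related vital-sign changes in the earlier 12-week placebo-controlled study of the inhaled drug. This stands as far as it goes: the shifts of 5 and 10 bpm above are illustrations, not expectations. But the first statement is general pharmacology, and the second comes from pulmonary arterial hypertension and does not mention ECG findings. Neither settles the matter for PH-COPD.

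A reader might infer that ordinary visit-to-visit heart-rate variation biases the QT comparison. The design does not support that. Such variation falls on both arms, each ECG follows at least 5 minutes of rest, and the visit lists place the ECG ahead of the walk test (although the order is not stated to be mandatory). The result is noise.

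A reader might also infer that the planned QT results cannot be interpreted at all. That goes too far. SAP 10.7 tabulates heart rate and its change beside QT, so a shift in mean rate would be visible. Investigators classify each ECG, treatment-emergent abnormalities are counted by type, and clinically significant changes are reported as adverse events. What these do not supply is a correction of individual values: the correction is non-linear and applies to each tracing, and adjacent group means do not show how rate and QT moved together within a subject.

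Finally, nothing is lost for good. QT and heart rate are both recorded, and SAP Section 1 allows unplanned analyses to be reported in the study report. That limits the severity, but a derivation chosen after unblinding carries less weight than one written down beforehand.

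**Conclusion.** The point holds as a low-severity improvement. Both versions of SAP 10.7 present QT only in uncorrected form, and a treatment-related heart-rate change would mask or imitate a QT effect in those tables. On the assumed 400 ms and 70 bpm, the shift in QT is 8.6 ms at +5 bpm and 16.5 ms at +10 bpm (Bazett 23.9 ms at +10 bpm), with about 18 ms of QTcF prolongation hidden if QT is unchanged at +10 bpm. These sizes depend on the assumed corrected QT, starting rate and formula.

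The documents do not show that the drug changes heart rate in this population. The conclusion is only that the planned tables could not separate such a change from a QT effect ECG by ECG. The ECG summaries are descriptive, and the primary endpoint, power and Type I error are untouched.

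**What to change.** In SAP 10.7 and in its replacement text in SAP 12.4.7:

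- Derive QTcF = QT/(60/HR)^(1/3) for each ECG, using the QT and heart rate from that same tracing.
- Do this before same-day readings are averaged, because the QTcF of averaged inputs is not the average of the individual QTcF values.
- Present QTcF values and change from the respective baseline beside uncorrected QT, with the same visits, treatment grouping and baseline rule as the other continuous ECG variables.
- Add QTcF to the SAP abbreviation list.

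The cost is one derived variable and a few extra table rows. It needs no new ECG, no new data field and no change to the visit schedule. Protocol Section 10 allows changes in statistical methods made before database lock to be documented in the SAP without a protocol amendment.

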10.8 PULMONARY FUNCTION TESTS

Descriptive statistics will be presented by treatment group at baseline for the following parameters (absolute values and % predicted): FEV₁, FVC, TLC, and DLCO uncorrected for hemoglobin and lung volume. Additionally, descriptive statistics of the raw values and change

from the respective baseline will be presented for each post-baseline assessment by treatment received at the time of the visit.

10.9

[REDACTED]

[REDACTED]

10.10 OXYGENATION

10.10.1 Pulse Oximetry

Pulse oximetry measurements will be taken before, during, and after each 6MWT. These measurements include the collection of saturation peripheral capillary oxygenation (SpO₂) and heart rate (HR). Descriptive statistics of raw values and the change from baseline pre-walk, post-walk, and the lowest recorded SpO₂ (and associated HR) for each 6MWT will be presented by treatment received during time of assessment. The baseline value used to compute the change score of each follow-up measurement will be respective of the same timeframe of the follow-up value (ie, pre-walk baseline used for pre-walk follow-up).

12.4 CONTINGENT PARALLEL DESIGN ANALYSIS PLAN

The RIN-PH-304 study is an adaptive study with a (fully blinded) decision for design modification based on enrollment and missing data metrics. Following a formal and documented decision to switch from the Original Crossover Design to the Contingent Parallel Design, the following modifications will be applied to those sections specified in the main body of this SAP with the Original Crossover Design. To minimize repetition, this section will cover only those sections affected by a decision to switch to the Contingent Parallel Design, that is:

- If no modifications are required to a section in the main body of the SAP, no mention will be made below. For example, Section 2 (Study Objectives and Endpoints) requires no modification under switch to a parallel design.
- If a modification will be necessary, the affected section number and the replacement text are provided below. The updated text will then supersede the current text in the main body of the SAP. Text within an affected section that does not require modification will not be repeated below.

12.4.1 Study Design

Section 3.1: Approximately 314 eligible subjects will be randomized to either 12 weeks of active study drug or 12 weeks of placebo (Treatment Period 1 only). All subjects following the adaptive switch will be discharged from the study following 12 weeks of treatment. The second washout (Washout Period - Washout 2) and Treatment Period 2 assessments will not be conducted following the adaptive switch and any previously collected Period 2 data will be ignored for the primary analyses.

12.4.2 Interim Efficacy Analysis

Section 4.2: A single interim efficacy analysis will be conducted when 75% of the subjects (ie, ~235 subjects) have completed the 12-week Treatment Period if both of the following criteria are met: a) the expected time to randomize the final (314th) subject is greater than 6 months; b) at least 90% of the 6MWD data is present for Period 1: Baseline and Week 12 for these subjects.

Section 4.2.1: Prior to any planned interim analysis being performed, the following steps will be followed to estimate the expected time to randomize the final (314th) subject:

[REDACTED]

Section 4.2.2: If conducted with exactly 75% information fraction, the interim analysis will apply a 2-sided alpha level of 0.019, and at the final analysis at a 2-sided alpha of 0.044 with the overall Type I error rate at 2-sided alpha of 0.05; the actual information fraction at the time of the interim analysis will be used to calculate the 2-sided alpha level that will be applied. Efficacy boundaries for early stopping of the study for efficacy are based on an O'Brien-Fleming spending function (PASS 12, NCSS, Version 12.0). There will be no corresponding futility boundary for the interim analysis.

12.4.3 General Considerations For Data Analyses

Section 7: If the study design is changed to a parallel design, efficacy and safety summary tables will follow the general format that baseline and post-baseline data will be presented by the assigned treatment group when those data are observed. Treatments will be labeled as "Treprostinil" and "Placebo" to correspond with the assigned treatment group.

Efficacy and safety data collected after study discharge (after Period 1) will not be presented.

Section 7.1: If the study design is changed to a parallel design for this study, only the Period 1 baseline for efficacy measurements will be used. Except for actigraphy measurements, the baseline value will be defined as the non-missing value immediately prior to dosing with study drug for Period 1: Day 1. The baseline period for actigraphy measurements will be the last 7 days during the washout period prior to the day of dosing on Day 1. In the event that the washout period is less than 7 days then only the non-dosing days will be used to derive a baseline average.

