7 GENERAL CONSIDERATIONS FOR DATA ANALYSES

Given the crossover design utilized for this study, efficacy and safety summary tables will follow the general format that baseline and post-baseline data will be presented by the assigned treatment condition when those data are observed during the treatment period. Treatments will be labeled as “Treprostinil” and “Placebo” to correspond with the assigned treatment condition.

Any efficacy and safety data that are collected during the washout period between Periods 1 and 2 will be presented for the assigned treatment condition from Period 1. Any follow-up data collected after Period 2, while on this study, will be assigned to Period 2. Subjects who are not retained will not be replaced during the study.

For continuous variables, the summary statistics will include the mean, standard deviation, median, lower quartile, upper quartile, minimum, and maximum. Statistics will be expressed using the level of precision in which the variable was collected. For discrete variables, summaries will include the frequency and percent in each category. Whenever practical, categories of discrete variables will be ordered and labeled as they appear in the case report form (CRF), and all categories represented on the CRF will be included in summaries, even when they do not apply to any patients in the study.

For data collected on a fixed schedule, the nominal time point will be used for summarization. Evaluations from Unscheduled Visits are to be mapped to Scheduled Visits to the extent possible per the protocol-specified windows. Repeat or redundant observations within an assessment window and observations that do not fall within any predefined assessment window will be excluded from summaries. If an evaluation is repeated, such as to confirm an observed aberrant laboratory value, the analyses will use the later value if within the protocol-specified window.

Unless otherwise specified, all final statistical tests will be 2-sided at alpha level 0.05 if the interim analysis is not conducted, and 0.022, if conducted. All tables will be presented in landscape format. For practical reasons, the point size may be reduced to (but not less than) 7 point for tables that contain too much information to fit into a single page. SAS[®] version 9.4 or higher will be used. The Sponsor's Biostatistics Department will analyze the efficacy and safety data.

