10.2 ADVERSE EVENTS

Adverse events are recorded starting from the time each subject signs the ICF until the time a screen failure is documented, study completion, or early termination. All events recorded by the Investigators will be assigned a MedDRA PT and SOC. The most recently available MedDRA version before the database lock date will be used to assign preferred terms and system organ classes. All presentations will present data by treatment received at the time of the event.

Adverse events that occur during the Washout Period following Treatment Period 1 will be presented as having occurred on the treatment taken by the subject during Treatment Period 1. Similarly, AEs that occur during post-discontinuation follow-up will be presented as having occurred on the treatment taken by the subject during Treatment Period 2. Finally, AE tabulations will allow occurrences during low dose run-in and blinded treatment to be assessed (eg, low dose treprostinil, treprostinil treated, any treprostinil, placebo treated). Non-treatment emergent AEs observed outside of any study drug exposure will not be presented.

In addition, a limited number of presentations may be tabulated for AE data by both treatments received at the time of the event and treatment sequence, including the total rates by sequence.

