12.4.7 Safety Analyses

Section 10.1: Exposure to treprostinil and placebo will be calculated as the date of last dose minus the date of first dose plus 1. If the date of last dose of study drug was missing or unknown, the return date of study drug will be used as an imputed date. All analyses will be presented by treatment.

Section 10.2: Adverse events are recorded starting from the time each subject signs the ICF until the time a screen failure is documented, study completion, or early termination. All events recorded by the Investigators will be assigned a MedDRA PT and SOC. The most recently available MedDRA version before the database lock date will be used to assign preferred terms and system organ classes. All presentations will present data by treatment received at the time of the event. Non-treatment-emergent AEs observed outside of any study drug exposure will not be presented.

Section 10.5: Descriptive statistics for each clinical laboratory parameter (hematology, serum chemistry, and electrolytes) will be presented by treatment group at baseline, each post-baseline assessment, and End of Study visits for raw data and change from baseline.

Section 10.6: Descriptive statistics for vital signs (heart rate, systolic blood pressure, diastolic blood pressure, respiration rate, weight, BMI) will be presented for both Baseline Visits by treatment. The same statistics will also be presented for each post-baseline assessment and End of Study visits for the raw data and change from the respective baseline. Any clinically significant change from Screening Visit 1 was to be recorded as an AE.

Section 10.7: Descriptive statistics for ECG findings (sinus rhythm [present/absent], heart rate, PR interval, QRS duration, QT interval, interpretation [normal/abnormal]) will be presented by treatment group. Continuous variables will also be presented as the raw values and change from the respective baseline will be presented for each post-baseline assessment by treatment received at the time of the visit. Whenever more than one ECG evaluations are recorded on the same day, the data summaries will use the average of these readings.

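### After a switch to the parallel design, SAP 12.4.3 can be read to drop the Washout 2 and Period 2 safety data of subjects already crossed over; on the other reading some placement rules stay unclear

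*SAP*

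**What the plan says.** SAP 12.4.3 replaces parts of Section 7 if the study switches. Its rule is "Efficacy and safety data collected after study discharge (after Period 1) will not be presented".

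Three other parts of Appendix 12.4 bear on it:

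- 12.4.1 places discharge as follows: "All subjects following the adaptive switch will be discharged from the study following 12 weeks of treatment". On data already in hand it says that "any previously collected Period 2 data will be ignored for the primary analyses".
- 12.4.7, replacing Section 10.2, says of adverse events (AEs): "All presentations will present data by treatment received at the time of the event". The only AE exclusion it states is "Non-treatment-emergent AEs observed outside of any study drug exposure will not be presented".
- The opening of 12.4 explains how the appendix works: "Text within an affected section that does not require modification will not be repeated below".

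The main body has two rules for the washout between periods. Section 7 provides that "Any efficacy and safety data that are collected during the washout period between Periods 1 and 2 will be presented" under the Period 1 treatment. Section 10.2 provides that "Adverse events that occur during the Washout Period following Treatment Period 1 will be presented as having occurred on the treatment taken" in Period 1. Neither is restated in 12.4.

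**The concern.** For a subject treated wholly after the switch, discharge and the end of Period 1 are the same moment, and the 12.4.3 sentence is harmless. For a subject who had already crossed over they differ. Such a subject finishes Period 1, goes through Washout 2, enters Period 2, and leaves at Week 25 or at an ET Visit.

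The sentence names safety data explicitly and ties discharge to the end of Period 1. A programmer who follows the parenthesis would leave out these subjects' non-serious AEs and their laboratory, ECG, lung-function and oximetry results from Washout 2 onward. In the placebo-first sequence that includes the first blinded exposure to treprostinil. A programmer who follows the word discharge would keep them, and would then have to decide where some of them go. Two careful people could produce different safety tables from the same data.

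**Working it through.** **Do the data exist?** Yes. Protocol 10.2.1 judges the switch on data presence at Week 25, the end of Period 2. Protocol 3.1 and 5.2 call back subjects who are in Period 2 at the switch for an ET Visit. SAP 12.4.1 itself speaks of Period 2 data already collected.

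**Reading by the parenthesis.** All safety data after Period 1 are left out of the summaries. Against this:

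- 12.4.1 limits the Period 2 exclusion to the primary analyses. The limit would have little purpose if 12.4.3 removed everything.
- 12.4.7 uses treatment received for AEs and ECGs, and its one AE exclusion concerns events outside drug exposure. Period 2 events on treprostinil or placebo are not of that kind. The conflict is by implication, because 12.4.7 never names Period 2.
- The deaths listing in 10.3, untouched by 12.4, still asks whether the subject had received the other treatment.

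**Reading by discharge.** The data stay in. Their placement is then:

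| Data from crossed-over subjects | Governing text | Placement |
|---|---|---|
| Period 2 AEs | 12.4.7, for 10.2 | treatment received |
| Period 2 ECGs | 12.4.7, for 10.7 | treatment received |
| Laboratory shifts | 10.5, not altered on this | treatment received |
| Lung function | 10.8, not altered | treatment received |
| Oximetry | 10.10.1, not altered | treatment received |
| Descriptive laboratory tables | 12.4.7, for 10.5 | treatment group only; unclear |
| Vital signs | 12.4.7, for 10.6 | by treatment, with two baseline visits mentioned; unclear |
| Exposure | 12.4.7, for 10.1 | by treatment, with the main body's split by period dropped; unclear |
| Washout 2 data and AEs | 7 and 10.2, not restated | unclear |

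The Washout 2 row is open for a specific reason. The replacement for 10.2 repeats the main-body opening and omits the washout sentence. The 12.4.3 sentence stands where the Section 7 washout paragraph stood. Each omission can be taken as deletion, or as text that survives because unmodified text is not repeated. Treatment received does not settle it, because no study drug is given in washout.

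**Scale.** The claim is textual and rests on no figure. These numbers show only its order of size.

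1. Planned active arm (SAP 5.1, Protocol 5.1): 133 / 0.85 = 156.5, rounded up to 157 per arm and 314 in total, as stated. Planned active exposure: 157 × 12 / 52 = 36.2 patient-years.
2. Randomized at the check (Protocol 10.2.1): 0.75 × 136 = 102.
3. Assumption: 25% to 75% of the 102 had entered Period 2, and half of these were placebo-first. Active in Period 2: 102 × 0.25 / 2 = 12.75, about 13; 102 × 0.75 / 2 = 38.25, about 38.
4. Assumption: mean Period 2 exposure of 3 to 12 weeks. Low end: 12.75 × 3 / 52 = 0.7 patient-years. High end: 38.25 × 12 / 52 = 8.8 patient-years.
5. Against the plan: 0.74 / 36.2 = 2% and 8.83 / 36.2 = 24%.

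**The case against.** The best defence is that the operative words in 12.4.3 are about study discharge. 12.4.1 places discharge at 12 weeks only for subjects following the switch, and the Protocol keeps crossed-over subjects in the study until Week 25 or an ET Visit. On that view nothing is lost, and 12.4.7 and the unaltered sections place most of the data. This is a reasonable reading, possibly the intended one. It does not explain why the parenthesis equates discharge with the end of Period 1, and it leaves the last four rows of the table open.

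The consequence is also limited. It arises only after a switch. Safety analyses are descriptive (Protocol 10.3.4, SAP 10). The listings of serious AEs (SAP 10.2.5) and deaths (SAP 10.3) remain on either reading. The unblinded Data Safety Monitoring Committee follows safety throughout (Protocol 10.7). All of this stands and holds the severity down.

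Four stronger readings should be resisted.

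- A reader might infer that 12.4 gives no rule at all for Period 2 safety data. The table shows that it does for AEs, ECGs, laboratory shifts, lung function and oximetry.
- A reader might infer a flat contradiction between 12.4.1 and 12.4.3. They differ in scope: one concerns primary analyses, the other presentation.
- A reader might infer a breach of Protocol 10.6. It promises only scientifically relevant data, which leaves discretion.
- A reader might take all 102 subjects as crossed over and completed, giving 51 on active drug, or 51 / 157 = 32% of the planned arm. A switch argues against that. If all 102 are the denominator, 0.85 × 102 = 86.7, so at most 86 could have Week 25 walk data and at most 86 Week 25 actigraphy.

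**Conclusion.** The point holds as an ambiguity with a real downside. One natural reading of a stated rule drops blinded, on-treatment safety data that the rest of Appendix 12.4 appears to keep. The other reading keeps them but does not settle Washout 2 attribution, descriptive laboratory and vital-sign tables, or exposure.

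The size is about 13 to 38 subjects on active drug in Period 2 and about 0.7 to 8.8 patient-years, or 2% to 24% of the planned active exposure. Those figures rest wholly on the assumed share in Period 2, equal sequences and the assumed mean exposure, none of which the documents settle for the time of the switch. The SAP's lists of tables, listings and figures (12.1 to 12.3) were not in the text reviewed, so the planned outputs could not be checked. Severity is minor to moderate. The primary analysis is not affected.

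**What to change.** Before unblinding, amend SAP Appendix 12.4 as follows.

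- In 12.4.3, restrict the safety part of the exclusion to data collected after a subject's actual final or ET visit. Leave Period 2 efficacy data to the rule already in 12.4.1.
- Add that safety data of subjects who crossed over before the switch, up to the Week 25 or ET Visit, are tabulated separately from the Period 1 randomized comparison. Period 2 data go by treatment received. Washout 2 data go under the Period 1 treatment, with the main-body rules in Sections 7 and 10.2 stated to be retained. Exposure is computed within period.
- In the 12.4.7 replacement for Section 10.6, correct the mention of two baseline visits to match. It is probably carried over from the crossover text.

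The cost is a few sentences and a few extra descriptive tables from data already collected.
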